Adverse effects of prokinetics can include diarrhea, which is one of the symptoms of SIBO¹⁹. Cholestyramine or other bile acid sequestrants are suggested as treatment options for diarrhea¹⁹, however it should be noted that these drugs can cause constipation, nausea, flatulence, bloating and abdominal pain.

It is thus obvious that there are many limitations in terms of the literature regarding treatment of SIBO. Rifaximin, the antibiotic best studied, is in fact a fairly expensive drug, not readily available or covered by public insurers in many countries. Although many antibiotics may be used in clinical practice²⁰, almost none have been carefully validated. There are, to our knowledge, no studies demonstrating how to treat relapses or first drug failures, how long to treat, how often to cycle antibiotics for relapses, or when to add other non-antibiotic agents. There are no specific trials in SSc that we could find and none were in fact included in the systematic review.

Pragmatic, multicentre, cluster, cohort randomised controlled treat-to-target trial for treatment of small intestinal bacterial overgrowth in systemic sclerosis (SSc) – A Pilot Project

The study: What will the full project look like if the pilot is successful?

What is/are the principal research question(s) to be addressed? We will determine if a structured, treat-to-target algorithm based on treatment response and relapse performs better than standard care for the treatment of symptoms SSc-SIBO.

Overview: This will be a 3 year, pragmatic, multi-centre, cluster, cohort randomised controlled treat-to-target (T2T) trial of SIBO. The pragmatic aspect relates to the intent to test the effectiveness of the T2T SIBO intervention in routine clinical practice in order to maximize applicability and generalizability. Our research question is *whether our proposed T2T SIBO intervention actually works in real life*. The intervention will be evaluated against standard care, in routine practice settings. As in most pragmatic trials, our outcomes will be mostly patient-centered^{21,22}. There will be a setup period of 6 months, recruitment over 1 year with a follow-up of one year and an additional 3 months for data analyses.

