For the target for “success” we will use the GSS questionnaire which will be administered on paper when the patient visits the doctor’s office for follow-up. In the study validating the GSS in SSc-associated SIBO, patients in whom the breath tests became negative after treatment had a significantly lower total GSS score than those with SIBO who did not become breath test

Pragmatic, multicentre, cluster, cohort randomised controlled treat-to-target trial for treatment of small intestinal bacterial overgrowth in systemic sclerosis (SSc) – A Pilot Project

negative (mean (range) 1.5 (0–9) vs. 8 (5–23), $p=0.001$)^{10,24}. None of the patients with eradication of SIBO had diarrhea. Hence, “no diarrhea plus a total GSS of < 5” will be the treatment target.

Meanwhile, those physicians randomly assigned to standard of care will also be informed of their patients who met eligibility criteria. They will not be aware of the detailed treatment protocol but will be informed of which medications are in the protocol eg antibiotics, prokinetics etc. They will be free to contact the patients at their convenience and to treat them in any way they deem suitable, preferably using these medications but at doses and frequencies according to their own wishes. As symptoms of SIBO tend to recur after short courses of treatment, and as the treatment protocol will be designed to adapt to this, we will follow each patient for one year from the time their physician was notified that they were eligible for the study. The primary outcome of the trial will be based on the patient reported outcomes regarding symptoms over the entire year.

What are the proposed primary and secondary outcome measures of the main trial?

Primary: The primary outcome is the total GSS score.

Secondary: Secondary outcomes include all GSS subscales. HRQoL will be assessed by the social scale of the UCLA GIT 2.0 and the NIH Promis29. Hospitalization for SIBO will be recorded during the 2 year study.

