What are the known safety concerns of the treatment(s), and are the concerns different for the proposed repurposed indication? This study will investigate the use of antibiotics and possibly other medications (eg. promotility, bile sequestrants, anti-diarrheals) for SSc SIBO treatment. For all antibiotics, hypersensitivity reactions such as exfoliative dermatitis, rash, urticaria, flushing, angioneurotic edema, pruritus, and anaphylaxis are a concern. Prolonged use may result in fungal or bacterial super-infection, including *C. difficile*-associated diarrhea and pseudomembranous colitis. Cholestyramine resin, which may be one of the drugs selected for use, should be used with caution in patients with triglyceride levels 250-299 mg/dL. Chronic use may be associated with bleeding problems (especially in high doses. Cholestyramine (especially high doses or long-term therapy) may decrease the absorption of folic acid, calcium, fat-soluble vitamins (vitamins A, D, E, and K), and iron. However, antibiotics and drugs such as cholestyramine are already in use for SIBO, although not in a standardized fashion, so the risks are not increased in this proposal. The use of certain promotility drugs is associated with a prolonged QT interval.

THE PILOT PROJECT

Objectives: To determine the feasibility of the full project. This will be a trial with 3 months of recruitment and 6 months of follow up for each case.

Specific Aims:

1. Determine if ethics committees perceive any major issues regarding the ultimate trial
2. Determine if the sites are approaching all eligible patients with study and offering consent forms.
3. Determine the signing rate of consent.
4. Determine patient adherence to web access for questionnaires.

Pragmatic, multicentre, cluster, cohort randomised controlled treat-to-target trial for treatment of small intestinal bacterial overgrowth in systemic sclerosis (SSc) – A Pilot Project

5. Assess our method for detecting eligible cases from web questionnaires.
6. Assess whether physician notifications are being sent out quickly after detecting eligible cases.
7. Assess the timeliness and completeness of physician receipt of notification of patient eligibility.
8. Assess physician adherence to treatment protocol:
 - a. how soon protocol patients are brought in to see doctor after receipt of notice.
 - b. does doctor record what he does accurately.
 - c. does he/she schedule return visits according to protocol.

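### The main trial's only listed hospital outcome is admission for SIBO, which rests on attributing cause in an open trial and cannot show admissions caused by treatment

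*Protocol*

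**What the plan says.** The Protocol section on proposed primary and secondary outcome measures of the main trial gives total GSS as primary. The secondary outcomes are the GSS subscales, two quality-of-life measures and one hospital outcome: "Hospitalization for SIBO will be recorded during the 2 year study". No admission for any other cause is listed.

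The Overview of the full project sets the calendar, in which the last 3 months are set aside for analysis: "There will be a setup period of 6 months, recruitment over 1 year with a follow-up of one year and an additional 3 months for". It also sets the period per patient: "we will follow each patient for one year from the time their physician was notified that they were eligible for the study". The primary outcome uses that same period: "The primary outcome of the trial will be based on the patient reported outcomes regarding symptoms over the entire year".

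The section on known safety concerns names harms of the treatments under test. For antibiotics, "hypersensitivity reactions such as exfoliative dermatitis, rash, urticaria, flushing, angioneurotic edema, pruritus, and anaphylaxis are a concern". It adds: "Prolonged use may result in fungal or bacterial super-infection, including" C. difficile diarrhea and pseudomembranous colitis. For prokinetics: "The use of certain promotility drugs is associated with a prolonged QT interval".

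Under the pilot's Safety Monitoring heading, suspected side effects are written on treatment sheets. Copies are requested after each visit and passed to the data monitoring board.

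**The concern.** An outcome restricted to SIBO admissions can record admissions that the algorithm prevents but not admissions that it causes. The comparison matters here because the algorithm is built to respond to recurrence, so exposure to antibiotics and other drugs could differ between arms, and the protocol links super-infection to prolonged use. The safety section asserts that risks are no higher than in current practice, but for admissions the outcome list gives no means of testing that.

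The restriction also makes the count depend on why someone judges the patient to have been admitted. Sites know their arm, and patients are told whether their site uses the treatment protocol or standard care. The same admission with diarrhea and abdominal pain could be classed as SIBO or as a drug effect. If that judgement leans differently in the two arms, the SIBO count moves with no real difference in admissions.

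**Working it through.** **1. The study period.** Inputs are from the Overview of the full project.

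- Recruitment + follow-up = 12 + 12 = 24 months = 2 years. This reproduces the two-year figure in the hospital outcome.
- Whole project = 6 + 12 + 12 + 3 = 33 months = 2.75 years, which the protocol rounds to 3 years.
- Follow-up per patient = 12 months from notification.

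Two years is therefore the calendar span within which the individual one-year follow-ups fall. The figures agree.

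What remains is a gap in wording: the hospital sentence does not say that an admission counts only within the patient's own year. If u is the month of notification, counting to the end of month 24 would give 24 − u months at risk. For u from 0 to 12 that is 24 down to 12 months, against a constant 12 months under the follow-up rule. If recruitment means consent, notification could come after month 12, and that patient's year would end after month 24. A stated window per patient settles both cases.

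**2. Overlap between SIBO symptoms and drug effects.** The symptom frequencies are those quoted in Background for SSc patients with SIBO. The drug effects come from the sections on current treatments and on safety concerns.

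| Symptom | Frequency with SIBO | Also named as an effect of |
|---|---|---|
| Abdominal pain or discomfort | 86.4% | bile acid sequestrants |
| Bloating | 77.3% | bile acid sequestrants |
| Constipation | 59.1% | bile acid sequestrants |
| Diarrhea | 50% | prokinetics; C. difficile after antibiotics |

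Each of these four symptoms has at least one drug-related cause in the protocol's own text, so presenting symptoms alone will often not settle why a patient was admitted. The protocol does not say who makes the attribution or by what rule. A rule may exist in the analysis plan, but it could not bring in admissions that the outcome excludes by definition.

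**3. Whether the side-effect route fills the gap.**

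- *Content.* The Safety Monitoring text refers to suspected side effects. It does not mention hospital admission.
- *Trigger.* Sheets are sent after a visit. Under First Appointments and Subsequent Appointments, protocol doctors are expected to see patients within a set time and keep to set intervals, while standard-care doctors decide whether and when to see the patient. The number of sheets per patient can therefore differ by arm.
- *Purpose.* The sheets go to the monitoring board so that serious harm can prompt a change. Nothing makes admissions recorded this way an outcome compared between arms.

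The route gives oversight of harm. It is a weak basis for comparing admissions between arms.

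**4. Size.** The protocol gives no admission rate for SIBO, for treatment harms or for any cause, so no numerical bias can be derived from it.

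**The case against.** A reader might infer that the two-year window contradicts one year of follow-up, or that patients notified early are counted for up to twice as long as those notified late. The documents do not support this. The calendar adds up, the follow-up sentence limits each patient to one year, and nothing says that anyone is observed beyond it. The natural joint reading gives every patient 12 months at risk. Only the request for clearer wording stands.

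A reader might also infer that treatment harms go unrecorded. That is too strong. Treatment sheets are used in both arms and have side-effect fields that reach a monitoring board. Although this text is in the pilot section, the pilot is said to reproduce the full trial. The named risks are also reduced by the exclusions for drug allergy that cannot be worked around, previous C. difficile infection and prolonged QT. It remains true that admissions caused by treatment are absent from the listed outcomes and that the sheet route does not name them.

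It can fairly be said that a cause-specific admission outcome with harms monitored separately is a defensible design. It is more defensible where attribution is blinded and harm is captured equally in both arms. The protocol describes neither for admissions.

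Finally, this is one secondary outcome of a future trial that depends on the pilot. None of the nine pilot aims uses hospitalization, and the pilot analysis is descriptive. This stands, and it limits the priority.

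**Conclusion.** The point holds for the definition of the outcome. As worded, the main trial's only listed hospital outcome depends on attributing cause in an open, site-randomised comparison, and it cannot show the net effect of the algorithm on admissions. It does not hold as a conflict over duration; there the sentence is only incomplete.

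The size cannot be stated, because it depends on admission rates and on differences in attribution between arms that the protocol does not give. The conclusion assumes that the outcome list is meant to be read as written and that the treatment sheet (Appendix 5, not in the text at hand) does not turn admissions into a compared outcome.

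Priority is low to moderate. The pilot's success criteria are unaffected. However, pilot sites keep their arm and pilot patients may be rolled into the full study, so it is better settled before that happens.

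**What to change.** Replace the hospital outcome sentence with:

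*All hospitalizations, with date and reason, will be recorded in both arms for one year from notification; hospitalization for SIBO and hospitalization for any cause (with gastrointestinal and treatment-related causes shown) will be reported side by side.*

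The any-cause count needs no attribution, so it checks the SIBO count and shows the net effect. The stated window gives every patient the same intended time at risk. Because visit frequency can differ by arm, admissions should be asked about in the same way in both arms and not only when a visit takes place.

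If the treatment sheet does not already capture admissions, add the item and try it in the pilot.

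The cost is one sentence of protocol text and, at most, one item on an existing form. The downside is recording some SSc admissions unrelated to SIBO or its treatment, which add noise to the any-cause count.

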The cluster component reflects the fact that treatment will be randomized to sites rather than patients. The cohort component reflects the fact that patients will be recruited from ongoing longitudinal cohorts via web-based interactions to determine eligibility. This aspect is a variant of the cohort multiple randomized controlled trial but in which only one trial will be performed (as opposed to multiple trials)²³.

In brief, SSc patients in the International Systemic Sclerosis Inception Cohort (INSYNC) sites, of which all participants in this trial will belong, are seen for study purposes on a yearly basis, to complete detailed, standardized protocols. Data are entered into databases and subsequently harmonized across all INSYNC sites. Although the initial purpose of INSYNC was to pursue research on inception cases, (defined as < 2 years disease duration), all INSYNC sites collect data on prevalent cases as well. Thus, for the purposes of this study, all patients seen, regardless of disease duration, will be assessed at a yearly visit to see if they are able to, and will consent to, accessing a web based Gastrointestinal Symptom Score (GSS) questionnaire that they will fill out at home at regular 3 month intervals. These questionnaires will both determine their eligibility for the SIBO study and will be the major outcome measure. Before the study begins, individual sites, which will total about 30 around the world, will be randomly assigned to be treatment protocol or standard of care arms. Every 2 weeks the study coordinator will have access to the patient questionnaire results. As soon as an eligible case is detected, ie a score of ≥ 5 on the GSS, the site will be notified of this patient.

Protocol treatment sites will be expected to see the patient within a pre-specified window of time. The doctors at that site will apply the treatment algorithm and will make decisions about response to treatment based on the algorithm and on specific patient answers to questionnaires. The treatment protocol will only be made available to IRBs, not to any site personnel before randomization. This was derived from a survey of rheumatologists in many countries and gastroenterologists, mostly in North America, who were asked multiple questions about how they would treat and follow up patients with suspected SIBO. (Appendix 1- Survey of Experts)

The algorithm created for this data represents the best consensus of those opinions.

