 - d. does he/she use in office questionnaires for treat to target.
 - e. does he/she base decisions on these questionnaires.
 - f. does he/she follow algorithm sequentially.
9. For control sites,
 - a. Record how soon protocol patients are brought in to see doctor after receipt of notice.
 - b. Assess whether the doctor accurately records what he/she does.

Methods: The pilot project will reproduce the full trial but at only 10 sites, 5 standard care and 5 treatment protocol.

Sites: We will choose 2 sites in Australia, 2 in the Netherlands, 2 in Canada, 2 in Spain and 2 in Germany. In each country one site will be randomly selected to be a protocol site and one standard care site. If a PI on the grant comes from a site, then another rheumatologist unaware of the treatment protocol will act as the treating physician. Sites in INSYNC are located in Australia, Canada, the U.S., the Netherlands, Spain, Germany and Sweden. This selection will give us representation from English and non-English speaking centers and from an array of countries with different medical cultures. It will also test our ability to monitor sites far from the study center in Montreal.

For the full study, these sites will retain their treatment status as assigned for this pilot.

The inclusion criteria for a site is that they agree in writing to adhere to the overall study protocol, and specifically that they agree, before seeing the treatment algorithm and before being assigned to protocol or standard care, to accept to treat according to the algorithm if they are assigned to that.

Patient Inclusion /Exclusion: Every patient who visits the participating doctor at a site over the recruitment period will be approached for consent to participate in the trial.

Inclusion: The patient must have an email address and must be computer literate enough to fill out the online questionnaires. From our experience where patients are asked if they have emails to see if they can participate, about 70% do. The online questionnaires will be available in the language of all countries participating.

Exclusions:

Pragmatic, multicentre, cluster, cohort randomised controlled treat-to-target trial for treatment of small intestinal bacterial overgrowth in systemic sclerosis (SSc) – A Pilot Project

- patients with allergies to any of the drugs in the protocol which cannot be substituted for another protocol drug, and this will apply to standard care patients as well.

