- patients with concomitant severe disease that would make it unlikely that they will survive for one year;
- patients with other illness or use of substances known to cause diarrhea;
- history of antibiotics in the 12 weeks prior to inclusion;
- history of intestinal pseudo-obstruction;
- inability to complete the symptom questionnaires;
- no functional level of written & spoken languages;
- previous *C. Difficile* infection;
- previous gastrointestinal surgery;
- prolonged QT interval;
- pregnancy or breastfeeding.

Screening for exclusions will be done at the site before the patient is consented. (Appendix 2- Exclusion Criteria Questionnaire)

As is typical of a pragmatic trial, we will keep inclusions broad and exclusions narrow.

Patients already on prokinetics will not be excluded but that prokinetic will be considered a failed drug and the treatment algorithm will proceed as such.

Consent and Patient Recruitment: Patients will be recruited at their regular yearly visit to their INSYNC physician or to any other participating physician. The study will be explained and they will be asked to sign a consent, (Appendix 3 – Consent Form), which will ask for their consent to be contacted by email. The email will contain a link to a website where they will be asked to fill in 2 forms, the UCLA GIT 2.0 and the GSS, on a monthly basis. They will be explained that their site will be using a specific treatment protocol or standard care and that the treatment protocol will employ much the same drugs that most physicians use for the problem of SIBO but in a very defined way. They will get a call or notice to see their doctor if they have evidence of SIBO based on their GSS test scores no matter what type of site they are assigned to.

Once a patient signs a consent, the global study coordinator will be informed that the patient is in the study via email. The email will include the patient's local study ID and their email address.

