Website Questionnaires: Subjects will access and fill in the GSS questionnaire which will be used both for screening for SIBO and for assessment of improvement with treatment. If the score of the GSS is ≥ 5 then the UCLA GIT and PROMIS GI questionnaires will also be triggered. (Appendix 4 – Questionnaires) They will be sent the link to the questionnaires via email from the central study coordinator. In this pilot, we will only screen subjects for 3 months total so the questionnaires will be filled in once a month for those 3 months. This will allow us to better assess the use of the website over a short period of time. Subjects will be notified immediately after consent is signed and thereafter once a month by email that they should fill in the questionnaire. A link will be provided. If the questionnaire is not filled out within 5 days an automatic repeat email will be sent out. We will repeat this every 5 days for a total of 3

Pragmatic, multicentre, cluster, cohort randomised controlled treat-to-target trial for treatment of small intestinal bacterial overgrowth in systemic sclerosis (SSc) – A Pilot Project

additional reminders. If there is no response after that the site coordinator will be informed and asked to phone the subject to determine and record the reason for the non-response and if the subject no longer wishes to be in the study they will be withdrawn.

Notification of Doctor of Eligible Case: If a score on the GSS is ≥ 5 , the computer will send an automatic notice to the office of the doctor and to the doctor him/herself telling them of this. The email notification will be repeated in 5 days to be sure that it has not been missed, and the provider will be asked to verify that it was received.

First Appointments: Upon receipt of the notice, the protocol doctors will be expected to make an appointment within the timeframe outline in the protocol. Standard care doctors, who will not know the details of this protocol, will decide on their own if and when to see the patient. Upon receipt of this notice the secretaries or clerks at the site will be asked to insert a treatment sheet (Appendix 5 – Treatment Sheet) in the doctor's chart. This sheet will be used to assess the timeliness of the first visit after notification, about the adherence of protocol doctors to protocol treatment and the types of medications and general pattern of treatment of the standard of care doctors.

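### The main trial's HRQoL outcome is the PROMIS-29, but the only PROMIS form in the described web schedule is PROMIS GI, and it is sent only while the GSS is 5 or more

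*Protocol*

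**What the plan says.** Under the heading "What are the proposed primary and secondary outcome measures of the main trial", the Protocol gives the total GSS as primary outcome. The secondary outcomes are the GSS subscales, HRQoL and hospitalization for SIBO. On HRQoL it says: "HRQoL will be assessed by the social scale of the UCLA GIT 2.0 and the NIH Promis29". This is the only mention of the PROMIS-29.

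The questionnaires are described in four other places:

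- **Overview of the full trial:** patients access a web-based "Gastrointestinal Symptom Score (GSS) questionnaire that they will fill out at home at regular 3 month intervals". No HRQoL form is scheduled there.
- **Consent and Patient Recruitment (pilot):** "they will be asked to fill in 2 forms, the UCLA GIT 2.0 and the GSS, on a monthly basis". No PROMIS form is mentioned.
- **Website Questionnaires (pilot):** everyone completes the GSS. If it is 5 or more, "then the UCLA GIT and PROMIS GI questionnaires will also be triggered". The section refers to Appendix 4 for the forms and adds that screening lasts 3 months, "so the questionnaires will be filled in once a month for those 3 months".
- **Subsequent Appointments (pilot):** the GSS is completed in the office at protocol visits, and no other form is named.

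Methods links the two studies: "The pilot project will reproduce the full trial but at only 10 sites, 5 standard care and 5 treatment protocol". Recruitment and follow-up period adds that pilot patients may enter the full study if the protocol does not change in major ways.

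**The concern.** The form listed as an outcome and the form listed for collection have different names. PROMIS GI is collected but serves no listed outcome. The PROMIS-29 is a listed outcome but has no stated time point. If both names are meant literally, pilot patients carried into the full trial would arrive without a PROMIS-29 score from the time they qualified, and that score cannot be obtained later.

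The trigger rule raises a second issue. A form sent only while the GSS is 5 or more is recorded only in patients who are still symptomatic. Whether HRQoL is observed at a later time point would then depend on how well treatment has worked.

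**Working it through.** No arithmetic is needed to establish the conflict. The check is to set every description of a patient questionnaire side by side.

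| Place in the Protocol | Study | GSS | UCLA GIT | PROMIS-29 | PROMIS GI |
|---|---|---|---|---|---|
| Outcome measures | Main trial | Primary outcome; subscales secondary | Social scale, as HRQoL | Named, as HRQoL | Not named |
| Overview | Main trial | Every 3 months | Not named | Not named | Not named |
| Consent and Patient Recruitment | Pilot | Monthly | Monthly, no condition | Not named | Not named |
| Website Questionnaires | Pilot | Monthly for 3 months | Only if GSS ≥ 5 | Not named | Only if GSS ≥ 5 |
| Subsequent Appointments | Pilot | At protocol visits | Not named | Not named | Not named |

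1. **Instrument.** The PROMIS-29 appears once, as an outcome. PROMIS GI appears once, as a triggered form. No row contains both, and no row gives a time for the PROMIS-29.

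2. **Which study is affected.** The PROMIS-29 column is filled only for the main trial. The pilot's nine aims cover ethics review, approach, consent, web adherence, case detection, notification, receipt, and physician adherence and recording. None uses an HRQoL score, and Data Analyses describes the statistics as descriptive.

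3. **Link to the full trial.** The pilot is to reproduce the full trial, its sites keep their allocation, and its patients may be carried over. Taking the text literally, a carried-over patient has a qualifying GSS, a UCLA GIT and a PROMIS GI, but no PROMIS-29.

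4. **Trigger.** The treatment target is absence of diarrhea together with a total GSS below 5. A patient at target therefore has GSS < 5, the condition GSS ≥ 5 fails, and no PROMIS form is sent at that time point. If p is the proportion of an arm with GSS < 5 at a given web questionnaire, at most 1 − p of that arm can supply a PROMIS value there. If treatment changes p, the arms are observed in differently selected subsets. This holds even if PROMIS GI is a loose name for the PROMIS-29.

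5. **UCLA GIT.** Consent and Patient Recruitment gives it to everyone monthly, while Website Questionnaires makes it conditional on GSS ≥ 5. Under the second rule, the other HRQoL instrument has the same selective observation as in step 4.

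**The case against.** The strongest reply is that the two texts concern different studies. The outcome list describes a proposed main trial, while the web schedule is that of a feasibility pilot, which already departs from the full trial in questionnaire frequency and length of follow-up. That is right, and no endpoint of the pilot is lost.

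The second reply is that the absence is partly silence. Appendix 4 is not shown, PROMIS GI may be shorthand, the main trial is only outlined, and the contents of the yearly INSYNC protocols are not given. This also stands. A reader might infer that the PROMIS-29 would never be measured at baseline or follow-up in either arm. The documents do not show that. They show only that the available text schedules no measurement.

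Other stronger readings also fail:

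- **Pain, fatigue and depression.** A reader might conclude that effects on these could not be shown. The Protocol does not say what the PROMIS-29 measures and lists none of the three as an outcome.
- **Web burden.** A reader might say that the pilot tests the wrong questionnaire burden. Element 4 concerns website use by all patients, whereas the PROMIS form reaches only those with GSS ≥ 5, expected to be about 25%.
- **Consent form.** The list of two forms comes from the Protocol's recruitment section. The consent form itself (Appendix 3) is not shown, so nothing can be said about its contents.

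What survives is that the PROMIS names conflict whatever the appendix holds, the trigger rule applies under either name, and the two UCLA GIT descriptions cannot both be followed.

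**Conclusion.** The point holds as an inconsistency to be reconciled, and it is minor. It affects one secondary outcome of the later trial, together with the schedule of the UCLA GIT, which supplies the other HRQoL measure. The loss of a PROMIS-29 baseline depends on two conditions: pilot patients are in fact carried over, which is to be decided after the pilot data are assessed, and PROMIS GI really is a different form from the one intended. The selective observation produced by the GSS trigger depends on neither the name nor carry-over. It would matter for the main-trial comparison if the pilot's web rule were kept.

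**What to change.** Before the pilot's website opens, or at the latest before any patient is carried over:

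1. Name the same PROMIS instrument in the outcome list and in Website Questionnaires. Either replace PROMIS GI with the PROMIS-29, or add the PROMIS-29 alongside it, or, if PROMIS GI is what is intended, drop the PROMIS-29 from the outcomes.
2. Give the HRQoL forms with the qualifying GSS as baseline. Repeat them at fixed outcome time points in both arms for every notified case, whatever the current GSS.
3. Make the form list in Consent and Patient Recruitment agree with Website Questionnaires, and state once whether the UCLA GIT goes to everyone or only to notified cases.

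The cost is wording in three sections, a change to the website's form list and send rule, and a few more items for notified cases. On the Protocol's expectation that about 25% of patients will score 5 or more, the remaining 100% − 25% = 75% or so would have no added PROMIS items.
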